8.1.3 Other study parameters (if applicable)

All ventilation and patient monitor parameters are recorded (see table 2). Ventilation support is checked for changes due to pressure, volume and timing changes, because these can influence the need for oxygen. Because the interaction is too complex to adjust for, it will be mentioned in the analysis, but only in a descriptive manner.

When the patients cerebral oxygenation is monitored with NIRS this data will be recorded as well and analysed to see if automated control of the FiO_2 will lead to an improved stability (lower SD) of the cerebral oxygenation.

Table 2: Measured parameters	during the study
------------------------------	------------------

PARAMETER	ABBREVIATION	SAMPLE RATE	DEVICE
Gestational age	GA	Ones	
Age	Age	Ones	
Birthweight	Bw	Ones	
Weight	Weight	Ones	
Gender	Gender	Ones	
Ventilation Measurements			
Oxygen saturation	SpO ₂	1 Hz	Fabian HFO
Pulse rate	Pulse	1 Hz	Fabian HFO
Fraction of inspired oxygen	FiO ₂	1 Hz	Fabian HFO
Inspired tidal volume	Vti	1 Hz	Fabian HFO
Expired tidal volume	Vte	1 Hz	Fabian HFO
Air leak	%Leak	1 Hz	Fabian HFO
Positive end expiratory pressure	PEEP	1 Hz	Fabian HFO
Peak inspiratory pressure	PIP	1 Hz	Fabian HFO
Respiratory rate	RR	1 Hz	Fabian HFO
Inspiratory time	Ti	1 Hz	Fabian HFO
Expiratory time	Те	1 Hz	Fabian HFO
End tidal carbon dioxide	EtCO ₂	1 Hz	Fabian HFO
Patient monitoring			
Oxygen saturation	SpO2		M540
Pulse rate	Pulse		M540
Respiratory rate	RR		M540
Non-invasive blood pressure	Nbp		M540
Heart rate (if available)	ECG		M540
Extra during HFO ventilation			
Mean airway pressure (HFO only)	Pmean	1 Hz	Fabian HFO
Pressure amplitude (HFO only)	Pamp	1 Hz	Fabian HFO

Additional parameters if available			
Cerebral regional oxygen saturation	cSrO2	1/5 Hz	Invos
Hero Score (Heart rate variability)	Hero	1 Hour	Hero
Transcutaneous Oxygen	TcO2	1 Hz	Sentec
Transcutaneous CO2	TcCO2	1 Hz	Sentec

8.2 Randomisation, blinding and treatment allocation

This study is not randomised nor blinded. It is impossible to safely blind the care giver for the given intervention. The patients are used as their own control to limit the variation and thus the number of patients that have to be included.

Each neonate included in the study will be monitored for 8 hours while receiving routine care. The patient then receives 8 hours of automated control of the FiO_2 . After the intervention there will be another 8 hour observational period during routine care is given. With this setup we can correct for patients that are worsening or improving during the time of the observations.

8.3 Study procedures

Routine care

FiO₂ is controlled by the care givers as normal

SpO2 is monitored by both the Acutronic Fabian HFO ventilator and the Dräger M540 patient monitor, but only the M540 gives alarms. All parameters measured by both devices is measured continuously, a complete list can be found in Table 2 together with the sample rates.

Alarms are set as normal.

Automated FiO₂

Alarms are set as normal, and the clinical staff is instructed to provide standard care. SpO_2 is monitored by both the Fabian HFO and the Dräger M540, but only the M540 gives alarms. All parameters as listed in Table 2 are logged.

The FiO_2 administered is controlled by the Fabian HFO with the PRICO algorithm. The clinicians are able to manually adjust the FiO_2 at any time they feel it is needed. The PRICO algorithm disables when either the ventilation is insufficient, or there is a problem with the pulse oximeter.

8.4 Withdrawal of individual subjects

Subjects can leave the study at any time for any reason if they wish to do so without any consequences. The investigator can decide to withdraw a subject from the study for urgent medical reasons.

When patients improve and no longer need additional oxygen, they will drop out of the study, if it occurs before the completion of the automated FiO₂ phase.

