8.4.1 Specific criteria for withdrawal (if applicable)

8.5 Replacement of individual subjects after withdrawal

Patients that are withdrawn from the study before its completion will not be replaced.

Ten percent extra patients are included to compensate for withdrawal or premature

drop-out due to an improvement of ventilation and no need of oxygen therapy $(FiO_2=21\%)$

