8.6 Follow-up of subjects withdrawn from treatment

Subjects that are withdrawn will not be followed.

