9.4 Follow-up of adverse events

All AEs will be followed until they have abated, or until a stable situation has been reached. Depending on the event, follow up may require additional tests or medical procedures as indicated, and/or referral to the general physician or a medical specialist. SAEs need to be reported till end of study within the Netherlands, as defined in the protocol

9.5 [Data Safety Monitoring Board (DSMB) / Safety Committee]

A DSMB or Safety Committee is not needed.

10.STATISTICAL ANALYSIS

All analysis will be done on a intention to treat, with reporting on the time that the automated algorithm was disabled and the number of manual adjustments to ensure that the algorithm was doing the fast majority of the adjustments. Every time the algorithm disables the reason is recorded and will be reported. All manual adjustments that are

performed during the automated control period will be assessed and the possible reason reported.

Because analysis are performed on a per time basis, missing data does not affect the outcome. The amount of missing data, if any, will be reported.

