10.1 Primary study parameter(s)

The efficiency of the PRICO algorithm will be assessed by comparing the time spend outside and deviation from the SpO₂ target range. This is done with the area under the curve, normalized to a one hour period [SpO₂*min per hour]. It is calculated by taking the SpO₂ value from the patient monitor, logged once every second and, when it is outside the SpO₂ target range, subtract the target. The absolute value of all deviations is added together and divided by the length of all the recorded data in hours. The significance will be tested with a repeated measurement ANOVA.

The number of collected data points per period will be reported to show any possible bias due to unmeasurable SpO₂ levels, malfunctions or other events. This will be reported as a percentage of time recorded.

When there is a significant difference between the first and last period, the argument will be made that the patient changed overtime. In that case the automated period will be compared with the best of the two observational periods.

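### Section 8.4 removes infants who come off oxygen before the automated block ends but not after it, which conflicts with the intention-to-treat and missing-data statements in section 10

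*Protocol*

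**What the plan says.** The design is a fixed sequence of three 8-hour blocks: manual, automated, manual (sections 3 and 8.2).

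- **Exit rule (8.4).** When infants improve and no longer need additional oxygen, "they will drop out of the study, if it occurs before the completion of the automated" phase. The rule covers the first two blocks only. The investigator may also withdraw an infant for urgent medical reasons.
- **Replacement (8.5).** "Patients that are withdrawn from the study before its completion will not be replaced". Instead, "Ten percent extra patients are included to compensate for withdrawal or premature" drop-out, and the section names FiO2 of 21% as such a case.
- **Follow-up (8.6).** "Subjects that are withdrawn will not be followed".
- **Adverse events (9.4).** "All AEs will be followed until they have abated, or until a stable situation has been reached".
- **Analysis set (opening of section 10).** "All analysis will be done on a intention to treat".
- **Missing data (opening of section 10).** "Because analysis are performed on a per time basis, missing data does not affect the outcome".
- **Primary measure and test (10.1).** The summed deviation outside the target range is "divided by the length of all the recorded data in hours", and significance is tested by repeated-measures ANOVA. If the first and last periods differ significantly, the automated period is compared with the better of the two.
- **FiO2 (8.1.2 and 10.2).** FiO2 is a secondary parameter, tested over the same three periods by the same method.

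**The concern.** Coming off oxygen happens after enrolment. During the automated block FiO2 is driven by the controller (8.3), so the exit can partly result from the intervention. Three consequences follow.

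First, the infants who remain are selected on oxygen need. FiO2 is itself an endpoint, and the rule cuts off its lowest values in the first two blocks but not in the third.

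Second, an infant who leaves before the automated block ends has no third block. Section 8.2 relies on that block to correct for infants who improve or worsen, and 10.1 uses it to choose the comparator. The drift check therefore runs without the clearest improvers.

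Third, dividing by recorded hours makes a short recording comparable in scale with a long one. It does not deal with the loss of the rest of a block, or of a whole later block, because of the infant's condition. The missing-data sentence is therefore wrong as a general statement.

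At stake are the size of the primary and FiO2 effects, and the meaning of an intention-to-treat label that the stated rules do not allow.

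**Working it through.** **1. The plan's own figures (section 4.4).** The inputs are a mean of 21 falling to 3, a difference of 18 %SpO2*min per hour; SD 30; 5% significance; and 80% power. Taking 30 as the SD of the within-infant difference and a two-sided test (neither is stated):

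n = ((1.960 + 0.842) × 30 / 18)² = 21.8, so 22 per stratum, as stated.

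Allowance for loss: 22 × 1.1 = 24.2, and the plan uses 24 per stratum, 72 in all. A 10% loss leaves 24 × 0.9 = 21.6 per stratum, or 72 × 0.9 = 64.8 in all. The allowance restores about the 22 needed, which shows that the plan does not count on leavers contributing.

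**2. The rules by block.**

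| Infant no longer needs oxygen in | Rule in 8.4 | Period values available at most |
|---|---|---|
| First manual block | leaves | part of block 1; no contrast |
| Automated block | leaves | block 1 and part of block 2 |
| Last manual block | stays | all three |

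Only the last row supplies the three values that a classical repeated-measures ANOVA needs.

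**3. Possible shift.** If a share p is lost and the lost infants' automated-versus-manual difference departs from that of completers by Δ, the completers' mean is off by p × Δ. The 10% is the plan's figure; Δ is assumed.

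- Δ = 30 (one planning SD): 0.10 × 30 = 3.0, and 3.0/18 = 17%.
- Half of the losses before the automated block (assumed), Δ = 30: 0.05 × 30 = 1.5, and 1.5/18 = 8%.
- Losses in opposite tails: the shifts partly cancel.

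**4. The same question with a graded link.** Let leaving depend on a latent normal variable with correlation r to the infant's paired difference (r is assumed). The shift is r × 30 × φ(z₀.₉₀)/0.90 at 10% loss.

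| r | Shift | Share of 18 |
|---|---|---|
| 0.3 | 1.75 | 10% |
| 0.5 | 2.92 | 16% |
| 1 | 5.85 | 32% |

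The sign can go either way. A simulation of 20,000 strata of 24 infants used a paired t test, a simplification of the three-period ANOVA. With leaving unrelated to the difference, type I error was 0.051 and power 0.76. With |r| of 0.3, 0.5 and 1, type I error was about 0.06, 0.07 and 0.15. If the infants who benefit most leave, power is 0.68, 0.63 and 0.56; if those who benefit least leave, power rises instead.

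**5. Room-air time and the primary measure.** With the 89–95% range in Table 1, an infant in room air at 98% accrues (98 − 95) × 60 = 180 %SpO2*min per hour, and at 96% it accrues 60. FiO2 cannot go below 21%, so no control method can correct this. Such time can count in the last manual block, while 8.4 removes the infant if the same happens earlier. One hour at 98%, averaged over an 8-hour block, adds 180/8 = 22.5 to that infant's value, more than the planned effect of 18.

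**The case against.** The best defence has five parts.

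- **Partial data.** No section says that data recorded before exit are discarded. The measure in 10.1 is per recorded hour, so a partial block yields a value, and section 10 requires missing data to be reported. Handling of incomplete periods may be set out in an analysis plan that is not shown. This stands in part: a reader might infer that the protocol prescribes a completers analysis, but it does not say so. That reading is implied by the loss allowance and by the chosen ANOVA.
- **Meaning of intention to treat.** The study is not randomised. The sentence goes on to disabled time and manual overrides, so it may only mean that each period is analysed as planned. This narrows the conflict but does not remove it, because the sentence covers all analysis while 8.4 to 8.6 take infants out.
- **Bias not demonstrated.** A reader might conclude that efficacy is biased, or biased in favour of the controller. The documents do not support that. If exit is unrelated to the paired difference there is no distortion, and 8.4 speaks of infants who improve, not of a momentary 21% setting.
- **Safety.** A reader might infer that harm in withdrawn infants goes unobserved. Section 9.4 covers all adverse events without exception and can be read as still applying. What remains is that 8.6 makes no exception for it.
- **The rule has a rationale.** Above-target time in room air says nothing about the controller, and 8.7 already sets aside cases at the FiO2 limit when judging controller problems. Simply logging on to 24 hours would add deviation that no one can correct. Nor would the routine monitor supply FiO2, which Table 2 takes from the ventilator alone. This stands, and it argues for treating such time alike in every block; the present rule does so only before the automated block ends.

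**Conclusion.** The point holds as an inconsistency among stated rules. Exit on coming off oxygen applies in two blocks of three, can depend on the controller in one of them, and leaves the section 10 claims on intention to treat and missing data unsupported. A completers analysis is the likely result, not a stated one.

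The possible shift is moderate: 3 of 18 (17%) at the plan's 10% loss and an assumed difference of 30, and about 10% to 32% over the assumed correlations. It is smaller if losses fall before the automated block or in opposite tails, and nil if exit is unrelated to the effect. The direction cannot be determined from the protocol. The loss rate, the effect of 18 and the SD of 30 are the plan's; everything about how leavers differ is assumed.

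**What to change.** 1. Define the analysis set in section 10 as every infant who started the automated block, analysed by planned period. Keep the per-hour area and the FiO2 recorded up to room air or withdrawal. Infants who leave in the first block give no contrast; count and report them.
2. Replace the repeated-measures ANOVA in 10.1 and 10.2 with a linear mixed model so that infants with incomplete periods contribute. Give completers only as a sensitivity analysis. The model relies on exit being explained by the recorded data, so that assumption should be stated.
3. Treat room-air time identically in all three blocks, for example by not counting above-target deviation while FiO2 is 21% in any block. Show the alternative as a sensitivity analysis.
4. Delete the sentence that missing data does not affect the outcome. Report exits by block and reason.
5. Reconcile 8.6 with 9.4 on follow-up of adverse events in withdrawn infants.

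Continued logging after room air is optional and not needed for any of this. The cost is a protocol amendment, slightly more analysis work, and blocks of unequal length, with short ones measured less precisely. No larger sample is required, and the clinical decision to withdraw an infant is unchanged.

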8.4.1 Specific criteria for withdrawal (if applicable)

8.5 Replacement of individual subjects after withdrawal

Patients that are withdrawn from the study before its completion will not be replaced.

Ten percent extra patients are included to compensate for withdrawal or premature

drop-out due to an improvement of ventilation and no need of oxygen therapy $(FiO_2=21\%)$

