An observational study conducted on our Neonatal Intensive Care Unit (NICU) has shown that infants on average spend only 54% of the time within the SpO_2 limits and 71 adjustments to the FiO₂ are made each day.

An automated controller (PRICO) has been developed that adjusts the FiO₂ based on the SpO₂. A study in a preterm lamb model has shown the effectiveness of this closed loop controller: less periods of desaturation and hyperoxia were demonstrated.

Objective: To test the safety and feasibility of a closed loop controller of the FiO_2 based on the measured SpO_2 in a NICU setting.

Study design: Neonates that are included will start with an 8 hour block of manual adjustment of the FiO₂. After completion of this block they will be switched to the automated control of the FiO2 for another 8 hours. After that they are switched back for another 8 hours of manual control, which is used to correct for any changes of the state of the neonate during the trial. For each ventilation type (high frequency , invasive and non-invasive) 24 patients will be included.

Study population: Neonates admitted to the NICU in the Erasmus MC, Rotterdam and Máxima Medical Centre, Veldhoven that are receiving respiratory support and a FiO_2 of more than 21%.

Intervention (if applicable): Automated control of the FiO₂ based on the measured SpO₂ during 8 hours.

Main study parameters/endpoints: The main parameter during the study is the time the SpO₂ spend within the target range. Secondary outcomes are the number of hyper and hypoxic events, average maximum and minimum SpO₂ during these events, number of FiO₂ adjustments (manual and automated) and cerebral oxygen saturation.

Nature and extent of the burden and risks associated with participation, benefit and group relatedness: There is no burden to the patient, and the risk is minimal. The same patient monitoring is used during the study as during routine care. The closed loop

algorithm is implemented in to the Acutronic Fabian HFO ventilator, so that no additional equipment is needed at the bedside.

The controller is designed so that it checks the input signals, the validity of the pulse oximetry and the quality of the ventilation. If any of the checked parameters is not within the specified limits the controller will not adjust the FiO_2 and give an alarm.

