4.4 Sample size calculation

The sample size calculation is based on the area under the curve for the SpO_2 . Giving a value that has a unit of [% SpO_2 *min]. A value of 30 can be reached by a SpO_2 of 30% outside of the target during 1 minute, or 30 minutes a SpO_2 that is 1% outside of the target. Values are normalized per hour.

During the animal trial conducted with this algorithm a reduction in the average of the area under the curve was found from 21 to 3 [%SpO₂*min per hour], with a standard deviation of 30 [%SpO₂*min per hour]. We accepted a significance level of 5% and a power of 80%. Because of the study design, each patient is its own control. Because of that only 22 patients are needed (Stata, StataCorp LP, USA). Because we want to show that the algorithm works in all 3 strata of ventilation we need three groups of 22 patients, and we expect a 10% dropout rate due to withdrawal or improvement in ventilation up to the point that additional oxygen is no longer needed, resulting in a total sample size of 72 patients.

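### At 10% dropout without replacement, 24 enrolled per stratum yield 21.6 evaluable infants, not the 22 that Protocol 4.4 requires; the power cost is under one point

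*Protocol*

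**What the plan says.** Protocol 4.4 sizes the trial on the area outside the SpO₂ target range. In the animal study "a reduction in the average of the area under the curve was found from 21 to 3", "with a standard deviation of 30" (both in %SpO₂·min per hour). The significance level is 5%, the power 80%, and the comparison is within patient: "Because of the study design, each patient is its own control". This gives 22 infants, required separately in each of three ventilation strata. For losses the section says "we expect a 10% dropout rate due to withdrawal or improvement in ventilation" and arrives at a total of 72.

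The Summary confirms the split: for each ventilation type "24 patients will be included".

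Section 8.5 sets the replacement rule: "Patients that are withdrawn from the study before its completion will not be replaced". It adds that enrolment has been raised by ten percent to make up for withdrawals and for infants who come off oxygen. Under 8.4, an infant who no longer needs oxygen leaves the study if this happens before the automated phase is complete. That includes the first 8-hour manual block.

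**The concern.** Section 8.5 rests its no-replacement rule on the claim that the allowance covers the expected losses. If 10% of those enrolled are lost, the number enrolled must be the number needed divided by 0.9. Adding 10% to the number needed gives less than that, and rounding the result down takes off a little more. With no replacement, nothing later in the protocol makes up the difference.

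The stake is the accuracy of a stated design property. The protocol wants to show that the algorithm works in all three strata, so 22 evaluable infants and 80% power are meant to hold stratum by stratum.

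**Working it through.** **Inputs (Protocol 4.4, 8.5, Summary).** Difference 21 − 3 = 18; SD 30; alpha 5%; power 80%; 22 needed per stratum; 3 strata; 10% dropout; 24 enrolled per stratum, 72 in total; no replacement. Sidedness is not stated. Two-sided testing, with 30 read as the SD of the within-patient difference, reproduces the plan's figure.

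**1. Reproduce 22.** n = (SD × (z₀.₉₇₅ + z₀.₈₀) / difference)² = (30 × 2.8016 / 18)² = 21.80, rounded up to 22. This matches. A one-sided test would give 18.

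**2. Reproduce 24.** 22 × 1.1 = 24.2, rounded down to 24; 3 × 24 = 72. The protocol does not show this step, but the ten percent extra in 8.5 fits it.

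**3. Inflation for 10% loss.**
- Per stratum: 22 / 0.9 = 24.44, rounded up to 25, or 75 in total.
- On the total: 66 / 0.9 = 73.3, rounded up to 74. Even 66 × 1.1 = 72.6 rounds up to 73.

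**4. What 24 delivers.**
- Per stratum: 24 × 0.9 = 21.6, which is 0.4 below 22.
- Overall: 72 × 0.9 = 64.8, which is 1.2 below 66.
- 24 keeps 22 only if at most 2 are lost, and 2/24 = 8.3%, below the assumed 10%.

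**5. Power by the plan's formula,** Φ(18/30 × √n − 1.96):

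| Evaluable per stratum | Power |
|---|---|
| 22 | 80.4% |
| 21.6 | 79.6% |
| 21 | 78.5% |
| Averaged over the number remaining from 24 | 79.5% |
| Averaged over the number remaining from 25 | 81.1% |

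The averages assume that each infant is lost independently with probability 0.10. The loss from 80.4% to 79.5% is 0.9 of a point.

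**6. Does the choice of formula matter?** A paired t calculation on the same inputs gives 76.5% at 22 and averages 75.5% from 24 enrolled. The level is lower, but the cost of the short allowance is again about one point.

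**The case against.** The strongest reply is that this is rounding. The unrounded requirement is 21.80, so the real gap is about 0.2 of an infant per stratum, and power stays within half a point of 80%. That stands, and it sets the weight of the point. The Summary, 4.4 and 8.5 also agree with one another on 24 and 72, and fixed over-enrolment without replacement is a legitimate choice. The slip is in the inflation step of 4.4; 8.5 only repeats the claim that rests on it.

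It can also be said that not every dropout is uninformative. Section 10 specifies intention to treat, and 10.1 divides by the length of recorded data, so an infant who leaves partway through the automated phase may still contribute. That is fair: 21.6 follows the plan's own convention of counting every dropout as lost, and is if anything pessimistic.

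Two stronger readings are tempting.

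- **That the trial will probably miss its size.** With independent 10% loss, the chance of keeping at least 22 of 24 is 56% in one stratum and 18% in all three. But the correctly inflated 25 reaches 22 only 76% and 45% of the time. A dropout allowance targets the expected number, so a test that the correct figure also fails more often than not across three strata does not measure the error.
- **That 8.5 is wrong to bar replacement of infants lost in the first manual block.** Such infants do give no manual-versus-automated comparison, and 8.5 makes no exception for them. But the protocol means the extra patients to cover losses of this kind, and it does not say how many occur before hour 8. Replacement would be acceptable; the documents do not make its absence an error.

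A possible worry about replacement is that it tilts the sample towards infants who do not improve early. Infants without an automated period are missing from the paired comparison whether or not they are replaced, so this does not count against it.

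**Conclusion.** The point holds as a small arithmetic correction to 4.4, repeated in 8.5. At the plan's own 10% loss, 24 per stratum yield 21.6 expected evaluable infants (64.8 of 66), so the claim that the extra tenth makes up for dropout is slightly untrue. The allowance that would make it true is 25 per stratum. Power per stratum is about 79.5%, against 80.4% at 22.

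This rests on a two-sided 5% test, on 30 being the SD of the within-patient difference, on independent losses at 10%, and on every dropout being non-evaluable. It does not support a conclusion that the trial is materially underpowered by the allowance or that the no-replacement rule is itself faulty.

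**What to change.** Either of two changes is enough; they should not be combined.

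1. **Restate the yield.** In 4.4 and 8.5, say that 24 per stratum, at 10% loss and without replacement, gives about 21.6 evaluable infants and about 79.5% power, and drop the claim of full compensation. This needs no extra patient; the cost is a slightly less favourable stated figure.
2. **Allow limited replacement.** In 8.5, let infants who leave before the switch to automated control at hour 8 be replaced within the same ventilation stratum. They have had no exposure to PRICO, so replacing them cannot select on response to it. The 21.6 and 79.5% figures should then be left out, because they would no longer describe the design. The cost is at most about two extra infants per stratum: 24 × 0.10 = 2.4 on average if every loss fell in the first block, before counting losses among the replacements.

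If the sponsor prefers to keep both the no-replacement rule and the claim that the allowance is sufficient, the number consistent with them is 25 per stratum (75 in total, 25 × 0.9 = 22.5 expected evaluable), at a cost of three infants overall.
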